### 1.3 POPULATIONS FOR ANALYSES

The sample from Aim 1 ( $n = 18$ ) will be used to refine procedures and the intervention protocol. The sample from Aim 2 ( $n = 40$ ) will be used to analyze feasibility and acceptability data and describe pre-post changes in patient-reported outcomes.

### 1.4 STATISTICAL ANALYSES

#### 1.4.1 AIM 1 ANALYSES

For Aim 1, all interviews will be audio recorded and transcribed using a transcription service. Study staff will annotate transcripts to identify which aspects of TRAC were the focus of comments. Annotated transcripts will be reviewed to refine proposed coding categories and create a coding categories dictionary. Coders will meet to compare results and resolve any discrepancies through consensus. Proposed initial coding categories are: Usability of delivery (e.g., perceived efficiency, ease), Length (appropriateness, acceptability), Content (appropriateness, helpfulness, relevance), and AYA specific education (e.g., AYA survivorship and risks of alcohol use for AYAs). If needed, data will be managed in NVivo software and we will engage the Markey Shared Resource Facility for additional coding support.

#### 1.4.2 AIM 2 ANALYSES

##### 1.4.2.1 FEASIBILITY

Enrollment: the number of AYAs enrolled divided by the number of eligible AYAs approached (hypothesized value = 60%).

Retention the percentage of AYAs who complete baseline and follow-up questionnaires (T0, T1; hypothesized value = 60%).

Adherence: the percentage of AYAs who complete at least 75% of sessions in 8 weeks (hypothesized value = 70%); alcohol monitoring hypothesized value = 70%).

We will calculate 95% CIs for feasibility measures to determine the range of estimates that are consistent with our data. We will use one-sample negative binomial probabilities and tests of binomial proportions to compare to hypothesized values. We will summarize reasons for ineligibility and refusal and compare AYAs who drop out or do not adhere by demographic and clinical characteristics, and baseline scores of the measures (e.g., PROMIS-29, alcohol use). We will investigate differences in AYA enrollment, retention, or adherence by sociodemographic and clinical characteristics (e.g., cancer type) to identify populations for a future study.

---

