- 5) meeting hazardous drinking criteria on the AUDIT-C questionnaire, defined as a score of 3 or higher for women/4 or higher for men (The AUDIT-C consists of items 1, 2, and 3 from the full AUDIT questionnaire);

Participants with severe psychopathology (psychosis, suicidal behavior, substance dependence) will be excluded from the study. The AUDIT questionnaire will be administered as part of screening to determine alcohol dependence; if survivors have a score of 20 or higher, they will be referred to UKMCC Social Work.

**RCT:** n=50, Intervention group (TRAC) n=25, and Control group (education and monitoring) n= 25. To be eligible to participate in the RCT, survivors must meet the following criteria:

- 1) diagnosed with cancer between age 15-39;
- 2) currently age 18-39;
- 3) 3 months - 15 years posttreatment (hormonal therapy allowed);
- 4) report unhealthy alcohol use in the previous 3 months, defined as:
  - a. exceeding moderate daily drinking levels (more than 1 drink/day for women, more than 2 drinks/day for men) at least 3 times in the past 3 months OR
  - b. engaging in heavy weekly drinking (more than 7 drinks/week for women, more than 14 drinks/week for men) at least once in the past 3 months OR
  - c. engaging in binge drinking (more than 3 drinks/sitting for women, more than 4 drinks/sitting for men) at least once in the past 3 months; OR
- 5) meeting hazardous drinking criteria on the AUDIT-C questionnaire, defined as a score of 3 or higher for women/4 or higher for men (The AUDIT-C consists of items 1, 2, and 3 from the full AUDIT questionnaire)
- 5) Reside in the United States

Just as with the Open Pilot, participants with severe psychopathology will be excluded from the study. The AUDIT questionnaire will be administered as part of screening to determine alcohol dependence; if survivors have a score of 20 or higher, they will be referred to UKMCC Social Work (if a patient at UK HealthCare). Non-UK patients will be provided with information for SAMHSA's treatment finder, national helpline, and local resources based on the zip code provided at the time of screening. Survivors who score a 20 or higher on the AUDIT questionnaire will not be eligible for the study, as this study is not designed to manage alcohol dependence and its immediate health risks.

Enrollment will begin February 2022 and continue through May 2023 or until the proposed participant pool is reached.

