## Objectives

List your research objectives. Please include a summary of intended research objectives in the box below.

Posttreatment rural AYAs are an underserved group at risk for increased alcohol use and poor access to interventions, ultimately leading to poorer physical and mental health. mHealth interventions are recommended for AYAs and have shown high acceptability and positive health effects. To address the lack of mHealth interventions for alcohol use among rural AYAs, we will adapt and pilot an existing mHealth intervention (TRAC) to reduce alcohol use. We will conduct the study in Kentucky, which leads the nation in cancer incidence and mortality, has a higher incidence of AYA cancers compared to other states, is 40% rural, and encompasses over 100 medically underserved areas. The study team has expertise in mHealth interventions, cancer survivorship, clinical trials, and AYA oncology. Thus, we are well-equipped to complete the following Aims:

1. Adapt and refine TRAC for rural posttreatment AYAs. We will conduct semi-structured interviews with key informants (N=14; 6 AYAs, 8 AYA oncology clinicians and community advocates), and conduct an open pilot study (i.e., fully implement the intervention) with a small number of patients (N=4; 2 TRAC, 2 control comparison) to adapt the content and delivery procedures of TRAC for rural AYA cancer survivors, resulting in TRAC-AYA.

2. Test the feasibility and acceptability of conducting an RCT of TRAC-AYA with AYAs (N=50; 25 TRAC, 25 control comparison). Comparison group will receive alcohol monitoring and educational materials. The primary feasibility outcome will be enrollment (=60% of eligible AYAs approached enroll). Secondary feasibility outcomes include retention (=60% complete follow-up) and intervention adherence (=70% complete =60% of intervention sessions; alcohol monitoring =70%). Acceptability will be assessed with mean ratings (scores =7 out of 10) of intervention relevance, helpfulness, and convenience. We will also obtain preliminary data on alcohol use frequency, quantity, binge drinking, and health (PROMIS-29).

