#### Study Procedures: Randomized Controlled Trial

To achieve Aim 2, we will conduct a pilot RCT of the TRAC-AYA intervention with a total of 50 participants (25 per condition).

Participants in the RCT will be enrolled in the study for a total of 10 weeks, whether they are in the intervention or control group. If participants are unable to complete monitoring or intervention tasks within the initial 4-week period, they will be given up to 6 weeks to complete the tasks before being considered noncompleters. The delayed post-test is delivered 4 weeks after completion of all monitoring/intervention tasks at 10 weeks.

Intervention (Group A) participants will complete 4 intervention sessions on a weekly basis, conducted via phone or videoconference (HIPAA-compliant Zoom), according to participant preference. These sessions will be audio recorded. Participants will also complete daily self-monitoring of alcohol use using mobile surveys and breathalyzers for 6 weeks. Control (Group B) participants will receive educational materials regarding alcohol use and will complete mobile monitoring of alcohol use in the same manner as Group A for 6 weeks. All RCT participants will complete a baseline assessment survey upon enrollment, a follow-up survey once all intervention/monitoring tasks are completed at 6 weeks, and a qualitative exit interview which will be audio recorded. All RCT participants will also complete a delayed post-test assessment at 10 weeks, 4 weeks after they complete the follow-up survey.

The total estimated maximum time commitment for RCT Group A (Intervention) participants is 13 hours, 45 minutes. The total estimated maximum time commitment for RCT Group B (Control) participants is 10 hours, 45 minutes.

All RCT participants will receive up to \$315 in Amazon e-gift cards for their participation.

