### 1.2 SAMPLE SIZE DETERMINATION

The sample size of 40 is based on the goal of estimating the probabilities and means for 3 feasibility outcome measures (enrollment  $\geq$  60% [primary], retention  $\geq$  60%, adherence [defined as  $\geq$ 70% completing at least 60% of sessions]). Assuming a negative binomial distribution and true probability of enrollment of 60%, the probability that we would have to approach 55 or more people to recruit 40 is  $<0.05$ . If we approach  $\geq$ 55 AYAs to enroll 40, it is unlikely the true probability of enrollment is 60% or greater, concluding a future efficacy study may not be feasible. Out of 40 AYAs, if the true probability of retention is 60% we expect at least 19 AYAs will be retained (i.e., probability of  $n \leq 19$  retained given true retention probability of 60% is  $<0.05$ ), so if more than 21 AYAs are not retained, an efficacy study may not be feasible. We have 80% power (using a 2-tailed alpha of 0.05) to detect an adherence proportion of 0.72 if we assume a null hypothesis adherence proportion of 0.50.

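### Retention is judged only over both arms combined, monitoring has one target with no arm stated, and randomised arm is not a listed comparison factor, so differential retention could go unassessed while the 60% target is met

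*Combined protocol and SAP*

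**What the plan says.** The Objectives section states Aim 2 as: "Test the feasibility and acceptability of conducting an RCT of TRAC-AYA with AYAs (N=50; 25 TRAC, 25 control comparison"). Enrollment is the primary feasibility outcome; retention and adherence are secondary.

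SAP 1.4.2.1 defines retention as "the percentage of AYAs who complete baseline and follow-up questionnaires (T0, T1; hypothesized value = 60"%), with no reference to arm. SAP 1.2 sets the warning on the total: "Out of 40 AYAs, if the true probability of retention is 60% we expect at least 19 AYAs will be retained", and "so if more than 21 AYAs are not retained, an efficacy study may not be feasible". Monitoring adherence in 1.4.2.1 has a hypothesised value of 70% and nothing more.

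SAP 1.4.2.1 then names the breakdowns. It will "compare AYAs who drop out or do not adhere by demographic and clinical characteristics, and baseline scores of the measures". A further sentence looks at enrollment, retention and adherence by sociodemographic and clinical characteristics. Neither sentence mentions randomised arm. The only between-arm analysis in the SAP is the t-test on pre-post change in 1.4.2.2.

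Both arms monitor. Under Study Procedures: Randomized Controlled Trial, control participants "will complete mobile monitoring of alcohol use in the same manner as Group A for 6 weeks". They receive educational materials in place of the four counselling sessions.

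**The concern.** A pilot meant to inform a definitive two-arm RCT should show whether each arm keeps its participants. A single combined percentage cannot separate two arms at 60% from one arm well above and one well below. The two experiences differ (counselling plus monitoring against education plus monitoring), so unequal retention is a reasonable thing to check.

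Two things are at stake. The first is what the pilot can say about an RCT with this comparator: a combined pass is weak evidence if one arm falls far short. The second is the TRAC-versus-control comparison of pre-post change in SAP 1.4.2.2. It needs both baseline and follow-up data, so differential dropout affects who is compared and the standard deviations carried into the next trial.

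**Working it through.** **Inputs.**
- Retention target 60% (SAP 1.4.2.1).
- Warning rule: more than 21 of 40 not retained, i.e. 18 or fewer retained (SAP 1.2).
- Sample size: the protocol's Study Population section has "n=50, Intervention group (TRAC) n=25, and Control group (education and monitoring) n= 25", while SAP 1.2 has "The sample size of 40 is based on the goal of estimating the probabilities and means for 3 feasibility outcome measures". Both are used below. Twenty per arm at n=40 is an assumption carried over from the protocol's 1:1 allocation.
- Arm-level retention rates are assumptions throughout; the documents give none.

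**The plan's own figure.** With X ~ Binomial(40, 0.60), SAP 1.2 puts the probability of 19 or fewer retained below 0.05. The exact values are:
- P(X ≤ 19) = 0.074, so the printed inequality does not reproduce.
- P(X ≤ 18) = 0.039, which is below 0.05 and matches the operative rule (more than 21 lost).

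The rule is consistent with the stated 5% level; the printed probability is off by one. The checks below use the operative rule, so the warning is silent at 19 or more retained.

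**What a combined 60% can contain (25 per arm).** (22 + 8)/50 = 30/50 = 60%, made up of 22/25 = 88% and 8/25 = 32%. Fisher's exact p = 0.0001. The exact 95% CI for 8/25 is 15% to 54%, which lies wholly below the target.

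**How often the combined figure passes.** The total retained is X₁ + X₂ with X₁ ~ Bin(m, p₁) and X₂ ~ Bin(m, p₂). Its distribution is the convolution of the two binomials.

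| Assumed true rates | P(total ≥ 30 of 50), m = 25 | P(total ≥ 19 of 40), m = 20 |
|---|---|---|
| 60% and 60% | 0.56 | 0.96 |
| 80% and 40% | 0.57 | 0.97 |
| 80% and 50% | 0.83 | 0.99 |
| 90% and 40% | 0.85 | 0.998 |

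The middle column is the chance of reaching the 60% target; the right-hand column is the chance that the warning stays silent. Each result is the same whichever arm has the lower rate. The first two rows are almost equal: the combined criteria respond to the average rate and hardly at all to the gap.

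**Monitoring.** If the 70% is an average over two equal arms, it is met by (100% + 40%)/2 = 70% or by (90% + 50%)/2 = 70%.

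**What by-arm reporting would show.** For 80% against 40% at 25 per arm, the 95% CI half-width for the difference is 1.96 × √(0.80 × 0.20/25 + 0.40 × 0.60/25) = 1.96 × √0.016 = 0.248. The interval is about 15 to 65 points, clear of zero. For a single arm at 15/25 the exact 95% CI is about 39% to 79%. A 40-point gap is therefore visible, but one arm's rate is known only roughly.

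**The case against.** A reader might infer that the control arm is the obvious one to fail. The documents do not support that. Maximum control time is lower (10 h 45 min against 13 h 45 min). Pay is the same in both arms at up to $315, of which up to $230 is for monitoring. The Study Design section expects that controls may gain from monitoring. Nothing in the text predicts which arm would lose more, or that either will. This objection stands, and the point is therefore stated for either direction.

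A reader might also infer that the plan has no means of showing how well the comparator retains people. That is too strong. The t-tests in SAP 1.4.2.2 need baseline and follow-up values, so per-arm completer counts would partly surface there. Exit interviews are held in both arms. But those counts are by-products, with no planned comparison or interpretation, and the interviews come after the follow-up questionnaire, so they mostly miss people who left.

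Three further limits stand. Retention is secondary, and the SAP 1.2 rule is a caution rather than a certificate: passing it does not declare the RCT feasible. Planned 95% CIs soften any pass/fail reading, although they too are for combined figures. Pooling of monitoring is read from silence: the Objectives section places monitoring within intervention adherence, so the 70% may mean TRAC only. In that case control-arm monitoring has no target at all, and the gap remains.

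Finally, the arm rates are invented for illustration. They show that the criteria do not register imbalance, not that imbalance is likely.

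**Conclusion.** The point holds as a gap in the planned analysis. SAP 1.2 and 1.4.2.1 judge retention only over all participants, leave the monitoring denominator undefined, and omit randomised arm from both lists of comparison factors. A difference as large as 88% against 32% is compatible with exactly meeting the retention target. At assumed true rates of 80% and 40%, the target is reached with probability about 0.57 (25 per arm) and the n=40 warning is silent with probability about 0.97 (20 per arm assumed).

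This limits what the pilot can conclude about an RCT with this comparator and bears on the between-arm contrast in SAP 1.4.2.2. It does not show that either arm will lose participants, and it does not touch the primary enrollment outcome. The finding covers the supplied text; a detailed protocol is listed among the attachments but is not in the file. It is worth correcting because the data are already being collected and the correction changes what the pilot can report.

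**What to change.** In SAP 1.4.2.1:

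1. State that monitoring completion is assessed in both arms, and give its denominator.
2. Report retention and monitoring completion for TRAC and control separately, each with a 95% CI, and the between-arm difference with its 95% CI.
3. Add randomised arm to the factors by which dropout, retention and adherence are compared.
4. State that the combined retention figure is interpreted alongside the per-arm estimates.

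While editing, reconcile the sample size (40 in the SAP, 50 in the protocol), since it sets the per-arm denominators, and correct the off-by-one in the SAP 1.2 retention probability.

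The cost is a few sentences and one extra table, with no new data, visits or participants. The price in precision is wide per-arm intervals, so the by-arm results should be presented as estimates and not as a second pass/fail test.

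### Relating baseline scores to session adherence through a yes/no cut discards the recorded 0-4 session count; using the count would gain about 0-17 points of power in an analysis that stays exploratory

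*Combined protocol and SAP*

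**What the plan says.** SAP 1.4.2.1 (Feasibility) gives the only analysis definition of session adherence: "the percentage of AYAs who complete at least 75% of sessions in 8 weeks (hypothesized value = 70"%). SAP 1.2 and Aim 2 of the protocol's Objectives set the cut at 60% of sessions instead. The protocol's RCT procedures state that "Intervention (Group A) participants will complete 4 intervention sessions on a weekly basis". The control arm has no sessions.

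After the definitions, 1.4.2.1 plans confidence intervals and tests against the hypothesized values, a summary of reasons for ineligibility and refusal, and then to "compare AYAs who drop out or do not adhere by demographic and clinical characteristics, and baseline scores of the measures (e.g., PROMIS-29, alcohol use"). No test, significance level, effect size or power is given for that comparison. The next sentence plans a look at differences in enrollment, retention or adherence across sociodemographic and clinical characteristics, with the aim of finding groups for a later trial. It does not say in what form adherence enters.

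The Records, Privacy, and Confidentiality section lists session completions among the tracking data, so the count will exist for each Group A participant. Nothing in the SAP mentions analysing it.

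On size, the protocol has "Intervention group (TRAC) n=25, and Control group (education and monitoring) n= 25", while SAP 1.2 begins "The sample size of 40 is based on the goal of estimating the probabilities and means for 3 feasibility outcome measures".

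**The concern.** A threshold is the natural form for a go/no-go criterion such as 70% adherent. It is a weaker response variable for asking who attends and who does not. The cut treats 0, 1 and 2 sessions as one outcome and 3 and 4 as another. In an arm of 20-25 people this leaves a comparison with a small non-adherent group and drops ordering that has already been recorded. If baseline drinking or PROMIS-29 is related to attendance, the split is usually less likely to show it and gives a less informative estimate. What is at stake is modest: how much the pilot can say about the relation of baseline scores to attendance. No feasibility decision depends on it.

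**Working it through.** **The plan's own adherence figure.** SAP 1.2 claims "80% power (using a 2-tailed alpha of 0.05) to detect an adherence proportion of 0.72" against a null of 0.50. With n = 40, the exact two-sided binomial test rejects at 13 or fewer or 27 or more, and power at 0.72 is 0.794, so the 80% reproduces. It concerns the one-sample target, not the predictor comparison, and it uses all 40 although only one arm has sessions. The same test has exact power 0.600 at n = 25 and 0.495 at n = 20. That is a separate matter; no power figure exists for the comparison discussed here.

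**What the cut means.** 0.75 × 4 = 3 and 0.60 × 4 = 2.4, which rounds up to 3. Both versions of the threshold therefore mean 3 or 4 sessions of 4.

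**Group sizes at the hypothesized 70%.**
- n = 25: 0.70 × 25 = 17.5 against 7.5, that is about 17-18 against 7-8.
- n = 20 (40 / 2): 14 against 6.

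**Power, continuous baseline score.** The documents give no attendance distribution or effect size, so these are assumptions:
- Latent attendance L is standard normal.
- The baseline score is X = rL + √(1 − r²)·e, with e standard normal and r from 0.3 to 0.6.
- L is cut into 0-4 sessions so that P(3 or more) = 0.70, under five attendance patterns.
- Tests are two-sided at 0.05, with 3,000 simulated trials per setting. The Monte Carlo standard error near power 0.5 is √(0.25/3000) ≈ 0.009.

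Spearman correlation of X with the count is compared with a t-test of X by adherent yes/no. At n = 25, the ranges over the five patterns are:

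| r | Count (Spearman) | Split (t-test) | Gain |
|---|---|---|---|
| 0.3 | 0.210-0.259 | 0.182-0.202 | 0.010-0.061 |
| 0.4 | 0.343-0.414 | 0.297-0.321 | 0.028-0.117 |
| 0.5 | 0.513-0.637 | 0.476-0.496 | 0.037-0.157 |
| 0.6 | 0.701-0.825 | 0.661-0.675 | 0.030-0.165 |

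The gain is thus 1 to 17 points in these 20 settings, with a median of 7-8. Against a Mann-Whitney test on the split it is 3 to 20 points, with a median of about 11. At n = 20 the gain over the t-test is 1 to 18 points.

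**Two patterns in detail (n = 25, r = 0.5, a separate run of 4,000 trials each).**
- Attendance 10/10/10/20/50% at 0/1/2/3/4 sessions: 0.602 against 0.477, a gain of 12.5 points.
- Nearly all-or-none (20% attend none, 65% attend all): 0.524 against 0.486, a gain of 3.8 points.

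If attendance is entirely all-or-none, the count and the split are the same variable and nothing can be gained; a rank method may then run slightly behind the t-test. This sets the lower end at about zero.

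**Power, binary characteristic (n = 25, latent difference 0.6-1.3 SD).** Mann-Whitney on the count gains 4 to 18 points over Fisher's exact test on the split, but −1 to 13 points over an uncorrected chi-square. The benefit therefore depends on which test the split would have used.

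**The case against.** The strongest reply is that there is no planned test here to lose power. Section 1.4.2.1 names none, the sentence stands beside a summary of refusal reasons, and describing who fails the study's own feasibility criterion is coherent. This stands in part. The fault is partly under-specification, and the yes/no table is a legitimate description. But non-adherence has no definition in the SAP other than the cut, so the plan as written leads to the split.

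Four stronger readings are tempting, and the documents do not support them:

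- *The split is made in the analysis that selects the future trial's population.* That purpose belongs to the following sentence, which also covers enrollment and retention, does not list baseline scores, and leaves the form of adherence open.
- *The loss is a fixed figure such as ten points.* It depends on the assumed attendance pattern, correlation and comparison test, none of which the SAP supplies.
- *Using the count rescues the analysis.* With the full count and n = 25, power is about 21-26% at correlation 0.3 and 34-41% at 0.4. Many characteristics would be examined, with no multiplicity plan.
- *The whole quoted comparison is affected.* It also covers dropouts, and adherence also includes alcohol monitoring, which both arms do. The point concerns session adherence in Group A only.

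**Conclusion.** The point holds as a minor improvement. The only definition of session adherence is a cut at 3 of 4, the planned comparison uses non-adherence as a group, and a recorded 0-4 count goes unused. For continuous baseline scores, the count gains about 0-17 points of power over a t-test split at n = 25. This assumes 70% adherence, latent correlations of 0.3-0.6 and a two-sided 0.05 level, and the gain is near zero when attendance is all-or-none. For categorical characteristics the gain is less certain and can vanish. The direction is well supported; the size rests on assumptions that the documents cannot settle. The threshold itself is sound for the feasibility target, and the predictor analysis is exploratory with either response.

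**What to change.** Keep the cut for the comparison with the 70% target and for the descriptive adherent/non-adherent table. Add to 1.4.2.1 that, in Group A, the predictor analyses use the number of sessions completed (0-4) as the response:

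- Baseline scores: Spearman correlation.
- Ordered or categorical characteristics: Wilcoxon or Kruskal-Wallis, or proportional odds.
- Each with an estimate and 95% CI, labelled exploratory.

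State that the dropout and alcohol-monitoring comparisons are separate and unchanged. The same edit should reconcile what the count depends on: Group A of 25 in the protocol against an implied 20 in the SAP; the 60% and 75% wording; and the eight-week window in 1.4.2.1 against the RCT procedures, which describe four weekly sessions with up to six weeks to complete them.

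The cost is SAP wording only, with no new data or participants. The downside is that results are expressed per session rather than as adherent yes/no, and there is one more set of exploratory results to report.
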